7.2. Study Population

7.3. Inclusion Criteria

- Men and women between 30 and 75 years attending the institution for a non-contrast cardiac CT scan (coronary calcium score) either by medical indication or voluntary for cardiovascular risk assessment.
- Signature of informed consent form

7.4. Exclusion criteria.

- Previously known chronic renal or hepatic insufficiency.
- Active chronic lung disease, defined as: exacerbated asthma, exacerbated COPD, or pulmonary fibrosis.
- Active and/or previous cardiovascular disease, defined as: previous acute myocardial infarction, stable or unstable angina, cerebrovascular accident, history of vascular interventions (coronary or other territory), heart failure, severe cardiomyopathies or valvulopathies.
- Uncontrolled hyper or hypothyroidism.
- Suprarrenal insufficiency.
- Previous surgeries in the last 3 months.

-
- Severe trauma in the last 6 months, defined as one that involved bone fractures and/or surgical interventions.
 - Known active cancer disease or under treatment (acute or preventive), or history of cancer disease without criteria for cure.
 - Known autoimmune disease active or in treatment.
 - Ongoing pregnancy, postpartum period of less than 12 months or breastfeeding.
 - Other serious illness with an estimated life expectancy of less than 12 months (according to the investigators).
 - Temperature greater than 37.5°C recorded by a thermometer or any acute infection caused by viruses or bacteria confirmed by a health professional in the previous 30 days.
 - Pathologies under immunosuppressive treatment

8. Procedures

8.1. Eligibility and informed consent

Patients will be recruited at the ENERI Medical Institute and at the outpatient clinics of the “La Sagrada Familia” clinic. Patients who meet the eligibility criteria will be approached by the main investigator or one of the study collaborators and the characteristics of the procedure to be performed, the risks of the associated procedures and the scope of the research to be carried out will be explained to them. After providing the necessary information and answering the questions of the participants, they will be formally invited to sign the informed consent.

8.2. Collection of clinical data and procedures in the baseline stage

At the time of inclusion in the study, the following epidemiological, clinical and complementary study data will be collected using questionnaires specially designed for this study:

Clinical data and medical history

- Contact data: Cell phone , landline, phone of an alternative contact, and E-mail address.
- Epidemiological data: date of birth, gender, ethnicity.
- Clinical history: Presence of any of the following pathologies: dyslipidemia, diabetes, high blood pressure, smoking, previous relevant diseases.
- Medications at the time of admission.
- Level of physical activity and diet.

Peripheral blood sample

2.5 milliliters of peripheral blood will be obtained by puncture of the antecubital vein in a PAXgene or Tempus tube (commercial tubes that contain a solution for the preservation of RNA) to obtain RNA. The patient must be fasting for 8 hours. Subsequently, the blood will be kept at room temperature for up to 48 hours, or at 4°C (in a refrigerator) for up to two weeks, until it is transferred to the laboratory, where it will be frozen at -20°C until it is processed (RNA extraction). .

Subsequently, the second additional peripheral blood sample (10 milliliters in EDTA) will be obtained to measure the complete blood count, glycosylated hemoglobin, hepatogram, lipid profile, among others. The primary tube for clinical laboratory analysis will be sent for analysis to a local laboratory (Stambulián).

Oral mucose swab (mouth swab)

To take the sample, the professional will be asked to rub a buccal swab against the inside of the patient's cheeks and gums, and to place it in a dry sterile 1.5ml eppendorf-type tube or with lysis buffer containing it will be labeled with the participant's ID and then place it in the refrigerator at 4°C waiting to be sent to the laboratory, where the DNA extraction will be performed. Subsequently, it will be stored in a freezer at -20°C.

Non-contrast cardiac computed tomography

ECG-triggered non-contrast cardiac CT ("coronary calcium score") will be performed using the same equipment in all patients, a spectral multidetector tomograph (IQon Spectral CT, Philips Healthcare, Best, The Netherlands). Non-contrast cardiac CT, associated with effective radiation doses of between 1.0 and 1.5 mSv (compared to approximately 5-7 mSv in a conventional chest CT), will be acquired using the following parameters: collimation 32 x 0.625 mm; voltage 120 kV; mAs adjusted according to weight (<60 kg= 30 mAs; 60 to 80 kg= 50 mAs; >80 kg= 80 mAs); rotation time 270 milliseconds; thickness 2.5 mm, with an acquisition time of approximately 0.18 seconds. Iterative reconstruction algorithms (iDose3) will be used for dose reduction.

12-lead electrocardiogram

All participants will undergo a 12-lead electrocardiogram, which involves the use of 10 electrodes for a correct reading of the electrical potential of the heart during a cardiac cycle. To carry it out, an electrode will be placed on each limb and 6 on the chest, generating 6 leads of the limbs that observe the heart from a frontal plane and 6 precordial leads that observe the heart from a horizontal plane. The risks of an EKG are minimal. Mild skin discomfort or irritation may be felt after the electrodes are removed. There is no risk of electric shock.

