Among the possible biomarkers mentioned in the previous paragraph are RNA molecules. Blood cells are subjected to all kinds of signals from the tissues they perfuse. These signals impact circulating cells, or even progenitors in the bone marrow, thereby modifying gene expression. Thus, the different states of a disease can present a set of differentially expressed genes. Various studies have confirmed the existence of genes expressed in patients with atherosclerotic disease. Alterations in gene expression in blood cells are evidenced in different states of predisposition to atherosclerosis (Ding et al., 2015), prognostic evolution (Holvoet et al., 2016), or response to treatment with statins (Kini et al., 2017). Furthermore, the expression of a set of genes has been associated with clinical variables to predict the severity of atherosclerotic disease (Y. Wang et al., 2019). Therefore, these studies show the existence of alterations in gene expression in patients with cardiovascular disease. It is currently claimed that these changes can be used in the

future as markers of the disease and its evolution (Marín de Evsikova et al., 2019; Chen & Stewart, 2016; Friede et al., 2015; Rhees & Wingrove, 2015).

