9.4. Analysis plan

For the description of the general characteristics of the study population, descriptive statistics such as means, medians and proportions will be used. To calculate the diagnostic performance of the method, the following will be calculated:

- True Positives (TP) or the probability that the test is positive since the disease is present

-
- True Negatives (TN) or the probability that the test is negative since the disease is not present.
 - False Positives (FP) or Type I Error
 - False Negatives (FN) or Type II Error
 - Sensitivity: $VP/VP+FN$
 - Specificity: $VN/ VN+FP$
 - Precision or accuracy: $VP/VP+FP$ or sensitivity + (1-specificity)

The diagnostic precision can vary between 0.5 and 1, where 1 represents a perfect diagnostic value and 0.5 is a test without diagnostic discriminatory capacity. An area under the curve (AUC) will also be performed to determine the diagnostic capacity of the trained algorithm.

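### Accuracy is reported only for statin users and non-users pooled, so the plan cannot separate a calcification signal from a treatment signal

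*Combined protocol and SAP*

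**What the plan says.** Five places in the protocol bear on this point.

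- **Section 4.4 (evidence in peripheral blood)** links treatment to the network's raw material. "Alterations in gene expression in blood cells are evidenced in different states of predisposition to atherosclerosis", and the same sentence adds "or response to treatment with statins".
- **Section 7.3 (inclusion)** admits people who come for a calcium score "either by medical indication or voluntary for cardiovascular risk assessment". It sets no condition on drug treatment.
- **Section 7.4 (exclusion)** has three treatment-related items: cancer under treatment, autoimmune disease under treatment, and "Pathologies under immunosuppressive treatment". Lipid-lowering drugs are not mentioned. The cardiovascular item reads "Active and/or previous cardiovascular disease, defined as: previous acute myocardial infarction, stable or unstable angina, cerebrovascular accident, history of vascular interventions", followed by heart failure and severe cardiomyopathy or valve disease. Calcification already known from an earlier scan is not listed.
- **Section 8.2 (baseline data)** collects "Medications at the time of admission", along with dyslipidemia, diabetes and hypertension.
- **Section 9.4 (analysis plan)** begins its accuracy analysis with "To calculate the diagnostic performance of the method, the following will be calculated". It then lists true and false positives and negatives, sensitivity, specificity, precision or accuracy, and an AUC. Section 8.4 feeds the network expression images only. Medication appears in neither section as an input, a stratum or an adjustment.

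**The concern.** If more people with CAC than without it take a statin, and statins leave a trace in blood-cell expression, a network trained to recognise CAC can gain discrimination by recognising treatment. Someone whose calcification was found on an earlier scan and who was then treated is eligible, so for some participants treatment could follow directly from the label.

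What is at stake is interpretation. The protocol's introduction aims to identify atherosclerotic patterns in the transcriptome, and section 4.1 motivates the work by early detection in people without symptoms. Discrimination that comes from treatment status tells us nothing new about a participant's arteries, and it disappears among people who are all untreated. A comparison with age, sex and risk factors alone would not reveal it, because a drug signature would count as new transcriptomic information. Nothing in section 9.4 would show whether this is happening.

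**Working it through.** The plan has no figure of its own to reproduce here. Section 9.3 justifies the 800 participants by training needs and gives no prevalence, effect size or precision. The question is how far a treatment signal could move the pooled AUC.

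**Inputs.** None of these is in the documents; all are assumptions. Treatment share without CAC is p0 = 0.15. Treatment share with CAC is p1 = 0.15, 0.30, 0.45 or 0.60. The AUC of the genuine expression signal among people of the same treatment status is 0.60. Treatment is detectable from blood either perfectly or with AUC 0.80.

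**Step 1: a score that detects treatment only.** With perfect detection, AUC = 0.5 + (p1 − p0)/2. With detection AUC At, AUC = 0.5 + (p1 − p0)(At − 0.5). For p1 = 0.45 these give 0.5 + 0.30/2 = 0.65 and 0.5 + 0.30 × 0.30 = 0.59.

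**Step 2: treatment added to a genuine signal, perfect detection.** Let the genuine score be normal with separation d = √2 × Φ⁻¹(0.60) = 0.358, independent of treatment given CAC status, and combined with treatment by likelihood ratio. With L the log odds ratio of treatment for CAC,

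AUC = p1(1 − p0)Φ[(d² + L)/(d√2)] + p0(1 − p1)Φ[(d² − L)/(d√2)] + [p1p0 + (1 − p1)(1 − p0)] × 0.60.

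For p1 = 0.45, L = ln[(0.45/0.55)/(0.15/0.85)] = 1.534, d² = 0.128 and d√2 = 0.507. The two Φ terms are 0.999 and 0.003. The AUC is 0.3825 × 0.999 + 0.0825 × 0.003 + 0.535 × 0.60 = 0.70.

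**Step 3: the same with imperfect detection.** Treatment status is replaced by a normal score that separates treated from untreated with AUC 0.80. The optimal combination was simulated with 400,000 people per class.

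| p1 (p0 = 0.15) | Treatment only, perfect | Treatment only, 0.80 | Pooled, perfect | Pooled, 0.80 |
|---|---|---|---|---|
| 0.15 | 0.50 | 0.50 | 0.60 | 0.60 |
| 0.30 | 0.575 | 0.545 | 0.64 | 0.61 |
| 0.45 | 0.65 | 0.59 | 0.70 | 0.63 |
| 0.60 | 0.725 | 0.635 | 0.77 | 0.67 |

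In the perfect-detection column, an AUC computed only from CAC-positive and CAC-negative pairs with the same treatment status is 0.60 in every row. That contrast with the pooled figure is what the plan cannot currently show.

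**Step 4: precision of a stratified estimate.** I used the Hanley–McNeil standard error at an assumed AUC A = 0.75: SE² = [A(1 − A) + (n1 − 1)(Q1 − A²) + (n0 − 1)(Q2 − A²)]/(n1n0), with Q1 = A/(2 − A) = 0.600 and Q2 = 2A²/(1 + A) = 0.643. Assume CAC prevalence of 30% to 50%, and treatment in 20% without and 50% with CAC (the same 30-point gap as the middle case). Then 520 to 568 of 800 are untreated. For example, with n1 = 120 and n0 = 448, 1.96 × SE = 0.054.

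| Predictions available on | 95% half-width, everyone | 95% half-width, untreated |
|---|---|---|
| all 800 (cross-validated) | 0.034–0.039 | 0.045–0.054 |
| 20% hold-out (160) | 0.076–0.088 | 0.100–0.121 |
| 10% hold-out (80) | 0.107–0.125 | 0.143–0.172 |

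The hold-out shares are those section 5.1 describes for the earlier development work. Section 9.4 does not say which scheme applies. The treated stratum is smaller, 232 to 280 of 800; the same formula gives about ±0.06 with predictions on all 800.

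**The case against.** The strongest reply is that the primary objective in section 6 concerns people without known cardiovascular disease, not untreated people. Such a population includes statin users, so a pooled estimate answers the stated question. This stands. A reader might infer that the pooled AUC is invalid or biased upward; the documents do not support that. Upward is the likelier direction if treatment is commoner with CAC, but treatment could also mask a disease-related pattern and lower the AUC.

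A reader might also infer that the network could match existing methods by detecting statins alone, since section 4.1 quotes AUCs of 0.60 to 0.65. That range describes prediction of cardiovascular risk, not detection of calcification, so it is no yardstick here. The larger figures in the table also need perfect detection of treatment and a wide gap in drug use. With no gap there is no effect.

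The evidence covers statins only; extending it to antiplatelet or glucose-lowering drugs is inference. The documents do not say how many participants will have previously known calcification.

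Finally, medication is recorded, so a subgroup analysis remains possible without a change to the plan. That is true, but an analysis chosen after the pooled result is known carries less weight, and the form has no dedicated item for earlier calcification.

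**Conclusion.** The point holds as a gap in the analysis plan. By the protocol's own account statins change what the network reads, statin users and people with known calcification can enter, and medication is collected. The only accuracy planned is pooled, and it cannot tell a calcification signal from a lipid-lowering signal.

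The possible distortion, relative to a within-status AUC of 0.60, runs from nothing to 0.17 with perfect detection of treatment and from nothing to 0.07 with detection AUC 0.80. It rests wholly on assumed drug-use rates and on treatment being independent of the genuine signal given CAC status. The documentary gap is certain; the size is not known. The pooled AUC remains a proper estimate for the clinic population described. What lacks support is carrying it over to untreated people or reading it purely as a calcification pattern.

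**What to change.** **In section 9.4**, keep the pooled AUC and prespecify, from the same out-of-sample predictions:

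- a treatment-stratified AUC, comparing CAC-positive with CAC-negative participants only within the same lipid-lowering status;
- AUC, sensitivity and specificity with 95% intervals, separately for participants taking and not taking lipid-lowering drugs at the blood draw;
- a sensitivity analysis that leaves out participants with previously known coronary calcification.

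Any statement that the test works in untreated people should rest on the untreated stratum.

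**In section 8.2**, code lipid-lowering treatment as yes/no and add one yes/no item for previously known coronary calcification. Coding other drug classes is optional.

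**Cost.** A few lines of text and two form items, with no new samples or procedures and no change to anyone's treatment. The untreated estimate is usable with cross-validated predictions on all 800 (about ±0.05) but imprecise in a 10–20% hold-out (about ±0.10 to ±0.17), so the prediction scheme should be named in the same place. Treated and untreated participants may also differ in age and risk, so a difference between strata would not by itself prove a drug signature, and the report should say so.

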5.2. Preliminary studies

We previously developed a clinical protocol with the aim of perfecting the methodology that will be used in this study. The initial goal was to develop blood collection, RNA isolation, library generation for sequencing, and RNA sequencing. Briefly, the preliminary results of these steps, performed on 540 samples from 3 different studies, are described below.

First, a robust methodology was established to obtain an RNA sample from peripheral whole blood (without cell separation). Samples were collected in PaxGene RNA tubes through antecubital vein puncture. No adverse effects were observed in this procedure. Samples were stored at -20°C until RNA extraction. This step was performed through the use of a specific kit (Thermo-Fischer). As a result, it was possible to consistently obtain RNA samples in sufficient quantities for sequencing in all cases. Then, the library was built, a process in which the RNA is transformed into cDNA (complementary DNA), from which the RNA corresponding to ribosomes and globin are extracted, fragmented, and finally the adapters are added at the ends. Again, the library construction was developed in a robust way for all the analyzed samples.

Subsequently, RNA sequencing was performed at a depth of 100 million reads. Between 20 and 25 thousand genes expressed in peripheral blood were detected in all the samples (n=540). In a series of patients, computed tomography was performed to determine the degree of calcification of the coronary arteries (Coronary Calcium Score, CCS). An analysis of gene expression in peripheral blood was performed and genes related to the degree of coronary calcification were found.

[figure not shown]

Figure 3: Preliminary results. We analyzed 38 samples from patients who had coronary calcium measured. The left panel shows the result of a PCA analysis where a moderate but significant reduction in dimensionality is found based on the extent of coronary calcium. The heatmap shows the differentially expressed genes between the two groups.

6. Study Objectives

Primary Objective

The primary objective of the study is to evaluate the diagnostic accuracy of peripheral whole blood transcriptomes analyzed by an artificial intelligence algorithm to detect the presence and extent of coronary calcification in individuals without a history of known cardiovascular disease.

Specific Primary Objectives

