7.1. Study Design

This trial will be a prospective observational study. A convenience sample will be carried out to include 800 patients who attend the ENERI Medical Institute, La Sagrada Familia Clinic, to undergo a cardiac CT without contrast (coronary calcium score), either for a medical indication or volunteers to an assessment of cardiovascular risk. The study will have a baseline stage in which a clinical evaluation will be performed, blood samples will be drawn for transcriptome analysis and laboratory analysis. Then, a DNA sample

obtained by swabbing the buccal mucosa will be taken. Subsequently, a non-contrast gated cardiac CT will be performed to assess the presence and extent of coronary calcification and other results of interest. At the end of patient enrollment, biological samples will be sequenced for in silico evaluation of the results. Finally, a 5-year clinical (telephone) follow-up will be carried out to collect data on the incidence of fatal and non-fatal cardiovascular events.

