8.4. Bioinformatic and computational analysis of the transcriptomics sample

The bioinformatic analysis of the sequenced samples will be performed from the .fastq files containing the raw data. These files will be fed to an *pipeline* analysis. It comprises a successive series of bioinformatic procedures, including sample quality control, alignment with the human genome and count of *reads* per identified gene. The transcripts to be identified correspond to messenger RNAs, non-coding RNAs, circular RNAs, and RNAs corresponding to the blood microbiome. The expression quantification of the transcripts is then transformed using a series of proprietary routines, to then be transformed into an image (US patent 62/944,063 (pending)). This image represents both the expression of the transcripts as a function of their expression level and the genomic position as well as the RNA subtype. The set of images, which represent the set of gene expression in peripheral blood, is subsequently entered into a neural network to generate training that classifies the samples according to it. All these bioinformatic and artificial intelligence procedures are carried out using *free use programs* (“*open access software*”) under a routine created by the study researchers, mainly using python for coding, and pyTorch for training the neural network.

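### Blood for RNA may go into either of two tube types and two holding routes, with no assignment rule and no stated recording, although the preliminary work describes one tube type only

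*Combined protocol and SAP*

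**What the plan says.** Section 8.2 (peripheral blood sample) has the RNA sample taken "in a PAXgene or Tempus tube". Until transfer to the laboratory for freezing at -20°C, the blood is "kept at room temperature for up to 48 hours, or at 4°C (in a refrigerator) for up to two weeks". No rule says which tube or which route applies to whom. The data listed for collection in the same section do not include tube type, holding route or holding time.

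Section 5.2 describes the earlier protocol, whose stated aim was to perfect the methodology for this study, and summarises 540 samples from three studies. There, "Samples were collected in PaxGene RNA tubes through antecubital vein puncture", and "Samples were stored at -20°C until RNA extraction". No second tube type and no holding step before freezing is described.

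Under section 8.4 the expression data are turned into images, and the image set "is subsequently entered into a neural network to generate training that classifies the samples according to it". Sections 8.3, 8.4 and 9.4 name no adjustment, stratification, balance check or sensitivity analysis for sample handling.

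**The concern.** The index test is the whole-blood expression profile, and the classifier is free to use any feature of that profile that separates the labels. Tube chemistry and time before freezing are technical features of the sample, not of the patient. If they leave a mark on measured expression, there are two possible consequences.

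- **Handling unrelated to CAC.** It adds noise that the network must learn around, in a test whose preliminary work covers one tube type only.
- **Handling related to CAC by an indirect path.** The network can gain apparent accuracy from it. Possible paths are recruitment setting ("Patients will be recruited at the ENERI Medical Institute and at the outpatient clinics of the" La Sagrada Familia clinic, section 8.1), referral route ("either for a medical indication or volunteers to an assessment of cardiovascular risk", section 7.1) and calendar period, for instance if tube supply changes during enrolment.

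In the second case a random split of the cohort carries the same association into both parts, so internal validation would look sound. If handling is not recorded, the analyst may later be unable to separate it from biology.

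**Working it through.** The plan gives no figure on this point to reproduce. Its only planning number, 800 patients (section 9.3), is not in dispute here.

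**Step 1: set the sections side by side.**

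| Item | Preliminary work (5.2) | This study (8.2) |
|---|---|---|
| Tube | PaxGene | PAXgene or Tempus |
| Holding before freezing | none described | room temperature up to 48 hours, or 4°C up to two weeks |
| Rule for which is used | not needed for one tube | none |
| Handling recorded | not described | not stated |

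The tube is a clear departure from what was piloted. For the holding route, section 5.2 is silent, so a departure cannot be shown.

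**Step 2: what tube type alone could yield.** Let p1 and p0 be the shares of one tube among patients with and without CAC. For a score that knows only the tube, counting ties as one half:

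AUC = p1(1 − p0) + ½[p1·p0 + (1 − p1)(1 − p0)] = 0.5 + (p1 − p0)/2, taking p1 ≥ p0.

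This assumes that the network recognises the tube perfectly. The documents do not give p1 or p0, so the values below are assumptions centred on 50%.

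- No difference: 0.5 + 0/2 = 0.50
- 52.5% against 47.5%: 0.5 + 0.05/2 = 0.525
- 55% against 45%: 0.5 + 0.10/2 = 0.55
- 60% against 40%: 0.5 + 0.20/2 = 0.60

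**Step 3: both handling factors.** Suppose holding route differs between CAC groups by the same amount as tube, independently of it. At 60% against 40% on each, the chances of 2, 1 or 0 markers are 0.36, 0.48, 0.16 with CAC and 0.16, 0.48, 0.36 without. Then AUC = 0.36(0.48 + 0.36) + 0.48(0.36) + ½(0.36·0.16 + 0.48·0.48 + 0.16·0.36) = 0.3024 + 0.1728 + 0.1728 = 0.648. At 55% against 45% on each, the same calculation gives 0.575.

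**Step 4: what an indirect path would need.** Assume two equal-sized recruitment settings, each using only one tube, with overall CAC prevalence p and a prevalence difference d between them. The difference in tube share between CAC groups is d/[4p(1 − p)].

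- At p = 0.5 the denominator is 1, so d of 10 or 20 points gives AUC 0.55 or 0.60.
- At p = 0.3 the denominator is 0.84, so the same AUCs need d of 8.4 or 16.8 points.

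If tube use is less sharply divided, the effect shrinks in proportion. When the setting mix differs by 20 points between CAC groups and tube use differs by 50 points between settings, the tube difference is 0.20 × 0.50 = 0.10 and the AUC is 0.55.

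**Step 5: after the change.** With one tube and no handling difference between CAC groups, the handling-only AUC is 0.50.

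**The case against.** The strongest reply is that nothing in the documents ties handling to CAC. This is one prospective cohort, not cases and controls collected separately. Section 7.1 puts the blood draw before the CT, and section 7.4 excludes known cardiovascular disease, so whoever picks the tube does not have the study CT result. That stands: it rules out a direct link through the study CT and leaves only indirect ones.

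The site path is also uncertain. Section 8.1 names two recruitment places, but section 7.1 can be read as one institution, and section 7.3 speaks of a single institution. Nothing says that tubes differ by place. This weakens the site path but not referral route or calendar period.

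There are partial safeguards: sequencing after enrolment ends (7.1), one library kit (8.3), sample quality control (8.4), and a manual of procedures that will cover blood extraction (9.2). The first three act after collection, and none of the four is said to fix the tube or the route. The data list in 8.2 is of questionnaire items, so laboratory records might hold tube type. The fair statement is that recording is not stated, not that it will not happen.

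A reader might also infer three stronger points that the documents do not support:

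- **That accuracy for CAC will be inflated.** This needs a tube effect on expression and a link with CAC, and neither is documented.
- **That a 20 to 30 point tube imbalance matches existing methods,** because section 4.1 quotes an AUC of 0.60 to 0.65. That range concerns identifying people at increased risk of developing or dying from cardiovascular disease, not detecting CAC on CT, so the two should not be compared.
- **That validation in this study is fixed as a 10 or 20% random split.** Section 5.1 says this of the laboratory's existing method, and section 9.4 specifies no split. The remark about random splits is conditional on one being used.

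**Conclusion.** The point holds as an uncontrolled and avoidable technical risk in the index test, not as a demonstrated bias. Two tube types and two holding routes are allowed with no assignment rule, no stated recording and no planned analysis, while the preliminary work describes one tube type.

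The size cannot be derived from the documents. Under assumed perfect tube recognition, a 10 or 20 point difference in tube use between CAC groups gives a tube-only AUC of 0.55 or 0.60. With no difference it is 0.50 and handling can only add noise. These values show what tube type alone could achieve. They do not show by how much the algorithm's final AUC would rise, since that depends on what the network already extracts and on how visible the tube is in the data.

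The change is worth making because it is cheap before or during collection, and missing handling data may be impossible to recover afterwards.

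**What to change.** In section 8.2, specify the piloted tube type for all participants. For every sample, record tube type, holding route, hours from draw to freezing and recruitment location.

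If both tubes have already been used, add to section 9.4:

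- a table of handling by CAC group;
- the AUC of a model that uses handling variables only;
- the algorithm's AUC within each tube type, with confidence intervals, or training on one handling stratum and testing on the other.

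Changing to one tube part-way would itself tie tube type to calendar period, so these checks would still be needed for the samples already taken.

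Do not rely on balancing handling between training and validation sets. That keeps any association between handling and CAC in both parts and so cannot expose it.

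Within-tube estimates may be imprecise. If 10 or 20% of 800 were held out (80 to 160 patients), the Hanley-McNeil 95% half-width for an AUC of 0.50 to 0.65 would be about 0.09 to 0.16 for the whole set, assuming CAC prevalence of 20 to 50%. It would be wider within one tube type.

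The cost is less supply flexibility, four data fields and a small amount of extra analysis.
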